2 PROTOCOL SYNOPSIS

C 4 1	TO 4 1
TILL 17	1111
Study	11116
~ • • • • • • • • • • • • • • • • • • •	

Effects of A3309, an Ileal Bile Acid Transport Inhibitor, on Gastrointestinal and Colonic Motor Functions in Patients with Functional Constipation

Study code

A3309-003

Principal Investigator

[name] M.D.

Professor of Medicine and Physiology,

Division of Gastroenterology and Hepatology,

Medical Director, Strategic Alliances, Mayo Clinic

Study period	Phase of development
Estimated date of first patient enrolled: January 2010	П
Estimated date of last patient completed: November 2010	

Study design

This is a single-center, randomized, parallel group, double-blind, placebo-controlled, dose response, pharmacodynamic and pharmacokinetic study evaluating the effects of A3309 on gastric, intestinal and colonic transit in patients with functional constipation. Doses of 15 or 20 mg A3309 or matching placebo will be administered orally once daily for fourteen (14) consecutive days.

Aim

To assess the dose related effects of A3309 on small bowel and overall colonic transit and bowel function in patients with functional constipation.

Primary endpoint:

Colonic geometric center at 24 h as measured by scintigraphy, as compared to placebo.

Secondary endpoints:

- 1. Colonic filling at 6 h measured by scintigraphy, as compared to placebo.
- 2. T_{1/2} of ascending colon emptying measured by scintigraphy, as compared to placebo.
- 3. Colonic geometric center at 48 h measured by scintigraphy, as compared to placebo.
- 4. $T_{1/2}$ of gastric emptying of solid
- 5. Assess the effects on stool frequency and consistency based on the Bowel Pattern Diary and effects on symptom parameters coupled to constipation as well as the overall treatment effect, as compared to placebo based on a six question survey given at the end of the pre-treatment period and the post-treatment period.
- 6. Evaluate the pharmacokinetic (PK) and pharmacodynamic characteristics for each dose of A3309.
- 7. Assess the safety and tolerability of A3309 administered as an oral tablet.

Number of patients planned

Twelve female patients with functional constipation in each treatment group for a total of 36 patients.

Diagnosis and main eligibility criteria

Patients with diagnosed functional constipation will be recruited from the local community by public advertisement placed within areas of Mayo Clinic or by a targeted mailing of an informational letter.

Methodology

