- Symptoms of constipation
- Overall treatment effects

Pharmacokinetic and pharmacodynamic analysis

Blood samples for analysis of pharmacokinetic (PK) parameters will be collected at Visit 4, before dosing and at 30, 60, 90, 120, 180, 240, 360, 480 minutes post dosing. Pharmacodynamic parameters (C4, total cholesterol, HDL, LDL and triglycerides) will be collected at Visit 1, Visit 4 and Visit 7.

PK parameters will be analyzed using conventional analyses by Covance, UK

Safety assessments

The following safety assessments will be performed:

- Laboratory safety tests, including a complete blood count (CBC), a comprehensive metabolic panel (CMP), coagulation studies and a urinalysis (UA) performed at Visit 1 study entry, Visit 4 transit scintigraphy and Visit 7 study completion. A urine screen for drugs of abuse will be performed once at Visit 1 study entry.
- A 12-lead ECG performed at Visit 1 study entry, Visit 4 and Visit 7 study completion.
- A physical examination by a study physician at Visit 1 study entry, Visit 6 and Visit 7 study completion and as necessary throughout the study.
- Weight and vital signs (including temperature, pulse, blood pressure and respiration rate) at every visit
- Urine pregnancy tests performed at Visit 1 study entry and within 48 hours prior to receipt of radiation during the abbreviated transit scintigraphy and post-study medication transit scintigraphy at Visit 2 and Visit 4, respectively
- Interview for concomitant medications and adverse events at every visit

Statistical methods

An analysis of covariance (ANCOVA) will be used to compare transit parameters and patient bowel pattern diary summaries (ie, stool frequency, mean stool consistency and mean ease of passage scores) among the treatment groups. The covariates considered for inclusion in the analyses are age, body mass index (BMI) and the corresponding baseline (pre-treatment) bowel pattern diary summaries. If necessary a suitable transformation for potential skewness in the distributions of measured responses or heterogenous variation among treatment groups may be used (e.g., ANCOVA on ranks or square root, transformed stool frequency.)

If the ANCOVA test for overall treatment effects for a given response has a p value less than or equal to 0.10, then both the 15 mg and 20 mg doses will be compared to placebo using Dunnett's test.

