24 STATISTICAL METHODS

24.1 Statistical considerations

An analysis of covariance (ANCOVA) will be used to compare transit parameters and patient bowel pattern diary summaries (i.e., stool frequency, mean stool consistency and mean ease of passage scores) among the treatment groups. The covariates considered for inclusion in the analyses are age, body mass index (BMI) and the corresponding baseline (pre-treatment) bowel pattern diary summaries. If necessary a suitable transformation for potential skewness in the distributions of measured responses or heterogenous variation amongst the treatment groups may be used (i.e., ANCOVA on ranks or square root transformed stool frequency.

If the ANCOVA test for overall treatment effects for a given response has a p value less than or equal to 0.10, then both the 15 mg and 20 mg doses will be compared to placebo using Dunnett's Test.

Since each of the primary endpoints assesses a separate hypothesis regarding the effects of A3309, no adjustment in the alpha level for testing multiple types of endpoints is anticipated, and a two-sided significance level of 0.05 will be used in each ANCOVA model.

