24.9 Assessment of sample size

Table 1 below summarizes data for the primary response measures and uses the (relative) variation, (CV%) to estimate the effect size detectable with 80% power based on a two sample t-test at a two-sided alpha level of 0.05. The effect size is the difference in group means as a percentage of the overall mean for each response and assumes 12 subjects per group. The ANCOVA should provide 80% power to detect similar (pairwise) differences using a pooled estimate of variation across all three groups and potentially even smaller effect sizes by adjusting for important covariates. The data from the scintigraphic transit studies are based on the same methods proposed for this study. There is no planned adjustment for dropouts. In these types of studies, we expect less than five percent dropouts. Missing data will be handled by standard imputation methods (e.g. use of mean data for all participants for that specific missing data), with appropriate adjustment of the degrees of freedom for each data imputed.

Table 6 Primary Response Measurement Summary

Assuming n=12/ group		Effect Size [‡] (%)		
		Detectable(N=12 per group) with:		
Response Type	CV%	80% Power (α =0.05)		
GE solids t _{1/2} min [†]	25	27		
GC @ 24 hrs †	35	37		
‡ Effect Size is the difference between means	as a percentag	e of listed mean		

^{†*} Based on data from previous studies (31,32,33) using similar methods to those proposed here. Transit data[†] from C-IBS studies (e.g. Renzapride, prucalopride, Tegaserod).

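### Step-down Dunnett would give more power to show the second dose than the default single-step Dunnett, at the same 5% familywise error; the overall F screen at 0.10 is harmless but redundant

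*Combined protocol and SAP*

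**What the plan says.** Section 24.1 (Statistical considerations) sets out two stages for each response analysed by ANCOVA. The first is an overall test of treatment: "If the ANCOVA test for overall treatment effects for a given response has a p value less than or equal to 0.10", the second stage follows, and "then both the 15 mg and 20 mg doses will be compared to placebo using Dunnett's Test". The synopsis repeats the rule: "then both the 15 mg and 20 mg doses will be compared to placebo using Dunnett's test". The next paragraph of 24.1 adds that "a two-sided significance level of 0.05 will be used in each ANCOVA model".

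The documents do not give a separate level for Dunnett's test, do not say whether it is single-step or step-down, and do not specify simultaneous confidence intervals. The design has three equal arms: "Twelve female patients with functional constipation in each treatment group for a total of 36 patients". Section 24.9 bases the sample size on an unadjusted two-sample t-test and expects that "The ANCOVA should provide 80% power to detect similar (pairwise) differences using a pooled estimate of variation across all three groups".

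**The concern.** Two features of the rule invite a closer look.

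- A screen at 0.10 in front of a procedure that already controls familywise error may do nothing. If so, it suggests a safeguard that is not there.
- Single-step Dunnett holds both doses to the stricter critical value, even after one dose has been shown to differ from placebo. The closed (step-down) form relaxes the second comparison at no cost in familywise error.

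With 12 patients per arm, and an aim that concerns dose-related effects of 15 and 20 mg, what is at stake is the chance of showing the second dose when both work.

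**Working it through.** **Inputs.** Three arms of 12 (synopsis), so 33 residual df without covariates and about 30 to 32 with one to three. CV 35% and effect 37% for the geometric center at 24 h (section 24.9, Table 6). Screen at p ≤ 0.10 (24.1). Assumed: single-step Dunnett, two-sided 5% familywise, because no variant or separate level is given.

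**The plan's own power figure.** Section 24.9 uses Table 6 "to estimate the effect size detectable with 80% power based on a two sample t-test at a two-sided alpha level of 0.05". The standardised effect is d = 37/35 = 1.057, with noncentrality d·√(12/2) = 1.057 × 2.449 = 2.59. Two-sided power at 0.05 is 70% with 22 df and 71% with the pooled 33 df, not 80%. The difference detectable with 80% power by the two-sample t-test is d = 1.197, which is 1.197 × 35% = 42%. That shortfall is a separate matter. Both effect sizes are carried below so that the comparison does not depend on it.

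**Step 1: can the screen change a Dunnett result?** With three groups, the overall F (2 numerator df) is the maximum of t²/2 over all treatment contrasts. So F ≥ t²/2 for each dose-placebo contrast.

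- Two-sided 5% Dunnett critical value, two comparisons, correlation 0.5, 33 df: 2.3105.
- A rejection therefore forces F ≥ 2.3105²/2 = 2.669, which is p ≤ 0.084.
- The screen needs only F ≥ F(0.90; 2, 33) = 2.471.

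Every Dunnett rejection passes the screen. With 30 df the two values are 2.693 and 2.489, and with 28 df 2.712 and 2.503. In simulation the screen blocked no Dunnett rejection in any scenario, including three-covariate ANCOVAs with arms as uneven as 8/12/12.

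**Step 2: single-step against step-down.** Single-step compares both |t| values with 2.31. Step-down compares the larger |t| with 2.31 and, only if that is significant, the other with the ordinary t value, 2.03. Results from 2,000,000 simulated trials per scenario (12/12/12, 33 df):

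| Scenario | Quantity | Single-step | Step-down |
|---|---|---|---|
| No effect | any rejection | 5.0% | 5.0% |
| One dose at +37%, other null | false rejection of the null dose | 2.7% | 4.1% |
| One dose with a very large effect, other null | false rejection of the null dose | 2.7% | 5.0% |
| Both at +37% | power per dose | 61% | 66% |
| Both at +37% | both doses | 46% | 56% |
| Both at +37% | at least one dose | 77% | 77% |
| Both at +42% | power per dose | 73% | 78% |
| Both at +42% | both doses | 60% | 70% |
| Both at +42% | at least one dose | 86% | 86% |
| Only one dose at +37% | power for that dose | 61.2% | 61.4% |

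Adding or removing the screen changes none of the single-step figures.

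**Step 3: where the extra rejections come from.** Each is a dose with |t| between 2.03 and 2.31 alongside a dose that has already passed 2.31. With both doses at +37% this happens in 56.1% − 46.0% = 10.1% of trials. In each of them the single-step simultaneous 95% interval for that dose, built with 2.31, includes zero.

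**The case against.** The strongest reply is that the planned method is valid. Dunnett's test controls familywise error at 5%, and the single-step form has intervals that agree with its decisions. The gain from step-down arises only when both doses work, and no section requires both to be shown. The study is a 36-patient Phase II pharmacodynamic trial whose results feed a later decision together with A3309-002 (section 19.2). All of this stands and limits the point to an improvement. It does not remove it: the plan specifies no simultaneous intervals that would be lost, and step-down is never less powerful at the same familywise error.

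Two stronger readings are tempting, and the documents do not support either.

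- A reader might infer that the 0.10 screen itself loses power. It does not: Step 1 shows that it cannot block a two-sided 5% Dunnett rejection in this design.
- A reader might take the 0.05 in 24.1 as the level of the overall F test, and conclude that F and Dunnett conflict on the primary endpoint. But 24.1 already gives the overall test its own threshold of 0.10, and section 9.2 defines the primary endpoint by comparison with placebo. The natural reading is that 0.05 governs the dose comparisons. One clarifying clause is enough.

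**Conclusion.** The point holds as a cheap improvement. Compared with the default single-step reading, step-down Dunnett adds about 5 percentage points of power per dose and about 10 points for showing both doses when both work at +37% or +42%. It adds nothing to the chance of at least one significant dose and about 0.1 to 0.2 points when only one dose works. Familywise error stays at or below 5%. The F screen is redundant wording.

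The conclusion rests on these assumptions:

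- Dunnett's test is single-step and at two-sided 5%. If step-down was intended, it only needs to be stated. At a 10% Dunnett level (critical value 1.98, below √(2 × 2.471) = 2.22) the screen could block rejections.
- The arms are near equal. The screen could also matter if the correlation between the two contrasts exceeded about 0.85, roughly a placebo arm of 2 against 12 per dose, which is not planned.
- CV is 35% and both doses have similar effects. The documents give no expected effect by dose, so the size of the gain is conditional on that.

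It should not be inferred that the plan inflates false positives or that the change would make a positive trial more likely.

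**What to change.** In section 24.1 and the synopsis, for every response analysed by ANCOVA and not only the primary endpoint:

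1. State that each dose is compared with placebo by step-down Dunnett at two-sided 5% familywise. The larger |t| is compared with the Dunnett critical value (about 2.31) and, if significant, the other with the ordinary t value (about 2.03), both at the actual residual df.
2. State that this comparison decides the result and, for the geometric center at 24 h, gives the primary verdict. The overall F test is descriptive.
3. Report step-down adjusted p-values as the decision, and label any single-step Dunnett intervals as estimation only.

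The screen should not be kept as a substitute for Dunnett: unadjusted t-tests behind an F test at 0.10 have 7.5% familywise error when neither dose works.

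The cost is a few sentences and no patients. The downside is the mismatch in Step 3: when a dose is significant only at the second step, its single-step simultaneous interval includes zero, and the report must say so.

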24.2 Analysis data sets

The primary analyses will follow the intent to treat (ITT) paradigm with all patients randomized included in the analyses. Those patients with missing response values will have their missing values imputed via the overall (patients with non-missing data) mean and a corresponding adjustment in the ANCOVA residual error variance degrees of freedom (subtracting one for each missing value imputed). A per protocol analysis of transit data will also be performed. The per protocol population consists of all patients having at least 80 % compliance with study drug and having participated in the transit evaluation.

Safety data will be presented for all patients receiving investigational product.

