Description: A patient will be withdrawn from the study if she develops diarrhea severe enough to require IV rehydration. The study will be discontinued if greater than 40 percent of patients develop diarrhea severe enough to require IV rehydration.

E. Study meetings/discussions

Identify method for documenting study discussions and meeting minutes, as well as follow-up communications.

Method: Decisions that alter the study procedures or the human studies aspects will be communicated to the IRB, CRU and sponsor and the review minutes will be documented in the regulatory binder.

Please note:

All DSMP's are subject to ongoing review and modification as new information concerning data integrity and safety issues become available. Proposals for revision of DSMP's may come from any source, including the PI of the study, the study coordinator, CRU nursing staff, or the CTSA – Research Resources Program Director. Revisions of the DSMP may be expedited per the decision of the Program Director or the Research Resources Review Panel (RRRP) Chair but requires approval by the RRRP at its regular meeting.

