Relative to the time of consumption of breakfast meal, abdominal camera images are initially obtained every 30 minutes for the first two hours, then hourly for the next six hours. At *about* 4 hours, a standard *chicken breast* lunch (chicken breast, potato, pudding and milk, the "Stanghellini" meal, 550 keal) will be given. Camera images will be taken at 5, 6, and at 8 hours post breakfast meal. At *about* 8 hours, the standard dinner (roast beef sandwich *snack*, sugar cookie and milk, the "Greydanus" meal, 750 keal) will be given. The patient will leave the CRU after the completion of the 8 hour image and will return the following two mornings in order to receive study medication and obtain 24 and 48 hour scans fifteen minutes later. The performance characteristics of this test are summarized elsewhere. Please see relevant references on the methods (6,7,8,9,10 29,30).

Reason for change: To correct a fault in regard to description of food intake during the visit. Update of reference list.

Section 24.2 Analysis data sets

Previous text:

The primary analyses will follow the intent to treat (ITT) paradigm with all patients randomized included in the analyses. Those patients with missing response values will have their missing values imputed via the overall (patients with non-missing data) mean and a corresponding adjustment in the ANCOVA residual error variance degrees of freedom (subtracting one for each missing value imputed).

Safety data will be presented for all patients receiving investigational product.

Revised text:

The primary analyses will follow the intent to treat (ITT) paradigm with all patients randomized included in the analyses. Those patients with missing response values will have their missing values imputed via the overall (patients with non-missing data) mean and a corresponding adjustment in the ANCOVA residual error variance degrees of freedom (subtracting one for each missing value imputed). A per protocol analysis of transit data will also be performed. The per protocol population consists of all patients having at least 80 % compliance with study drug and having participated in the transit evaluation.

Safety data will be presented for all patients receiving investigational product.

Reason for change: To add an analysis comprising patients having fully completed the transit evaluation without imputing any data as per the ITT paradigm.

Section 24.6 Stool frequency and stool consistency

Previous text:

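### The primary ITT analysis fills missing responses with a mean pooled over all three arms, which shrinks the drug-placebo difference when both doses work about equally; the degrees-of-freedom correction does not undo this

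*Combined protocol and SAP*

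**What the plan says.** Section 24.2 sets the primary population: "The primary analyses will follow the intent to treat (ITT) paradigm with all patients randomized included in the analyses". It then gives the missing-data rule: "Those patients with missing response values will have their missing values imputed via the overall (patients with non-missing data) mean", with one residual degree of freedom removed per value filled in. The synopsis (Analysis data sets) repeats this. Section 24.9 confirms that the mean is taken across arms, describing it as "use of mean data for all participants for that specific missing data". The same section states "In these types of studies, we expect less than five percent dropouts" and makes no allowance for dropout in the sample size.

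One analysis avoids imputation. Section 24.2 adds a per-protocol analysis of transit data and defines its set: "The per protocol population consists of all patients having at least 80 % compliance with study drug and having participated in the transit evaluation". The amendment log (Section 34.7) gives the reason: "To add an analysis comprising patients having fully completed the transit evaluation without imputing any data as per the ITT paradigm".

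The Data and Safety Monitoring Plan (Step 3, stopping rules) names one route to missing data that is linked to the outcome: "A patient will be withdrawn from the study if she develops diarrhea severe enough to require IV rehydration".

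**The concern.** A mean pooled over placebo, 15 mg and 20 mg says nothing about the arm the missing patient was in. Each filled-in value moves that arm part of the way to the grand mean, which amounts to partly assuming no difference between arms, the very question under test. The primary estimate then depends on which arm happens to lose a patient. It suffers most when that arm is placebo, because both dose contrasts use it.

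The degrees-of-freedom subtraction looks like a repair but acts only on the residual variance. It cannot change the arm means, and the contrast is still computed as if each arm had 12 real observations. At stake are a modest bias in the primary estimate and some lost power in a trial with 12 per arm and no dropout reserve.

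**Working it through.** **Inputs.** 12 per arm, 36 in total (synopsis); two-sided alpha 0.05, and a gate at p ≤ 0.10 followed by Dunnett's test (24.1); dropout below 5%, and for the primary endpoint a CV of 35% with a detectable effect of 37% (24.9). Five percent of 36 is 1.8, so the plan allows for at most one missing patient (1/36 = 2.8%). Assumptions: missing completely at random, no covariates, SD = 1, and the same effect d in both doses unless stated.

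**The plan's own effect size.** 37/35 = 1.06 SD. A two-sample t-test with 12 per group has 69.7% power there; 80% power needs 1.197 SD (41.9% at a CV of 35%). That mismatch is a separate matter. Both 1.06 and 1.2 SD are used below.

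**Estimate.** With m_j missing in arm j and m in total, the pooled mean is G = Σ(12 − m_j)μ_j / (36 − m), and the filled arm mean is [(12 − m_j)μ_j + m_j·G] / 12.

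- One on placebo: G = 24d/35. The placebo mean rises by (1/12)(24/35)d = 0.057d, so 94.3% is kept in both contrasts.
- One on 20 mg: (11 + 23/35)/12 = 97.1% kept for 20 mg; 15 mg is unaffected.
- Two on placebo (5.6%, above plan): 1 − (2/12)(24/34) = 88.2% kept in both.
- One on placebo and one on 20 mg: G = 23d/34, giving 91.7% for 20 mg and 94.4% for 15 mg.
- Two on 20 mg: (10 + 2 × 22/34)/12 = 94.1% for 20 mg.

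**Unequal doses.** With one 15 mg patient missing, G = (11μ15 + 12μ20)/35. This exceeds μ15, so the 15 mg contrast moves away from zero, when μ15 < 0.5·μ20. At 0.3 and 1.2 SD, G = 0.506 and the filled mean is (3.3 + 0.506)/12 = 0.317, or 106% of the true effect. Attenuation is therefore not universal.

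**Standard error, one placebo patient missing.** In units of 1/420, the 20 mg contrast puts weight −36 on each of 11 placebo values, +34 on each of 12 values at 20 mg, and −1 on each of 12 values at 15 mg. Its variance is (11 × 36² + 12 × 34² + 12 × 1²)/420² = 28,140/176,400 = 0.1595, so its true SD is 0.399. The reported SE uses √(1/12 + 1/12) = 0.408 times the residual SD. At d = 1.2 the expected residual variance after the correction is {32 + (11/12)[(1/11 − 1/35) + (1.2 × 24/35)²]}/32 = 32.68/32 = 1.021. The SE is then 0.408 × √1.021 = 0.4125, and 0.4125/0.399 = 1.03. The observed-data SE factor is √(1/11 + 1/12) = 0.417.

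In simulation the reported SE of an affected contrast is about 2–4% too large with one missing, and 5–7% with two when both fall in that contrast.

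**Power by simulation** (200,000 trials per case; 33 minus the number imputed as df). Each cell is the plan's rule / observed data.

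| Missing | Kept (20 mg) | Per comparison, d = 1.2 | Gate + Dunnett, d = 1.2 | Gate + Dunnett, d = 1.06 |
|---|---|---|---|---|
| 1 placebo | 94% | 0.77 / 0.80 | 0.67 / 0.71 | 0.56 / 0.60 |
| 1 on 20 mg | 97% | 0.79 / 0.79 | 0.71 / 0.71 | not run |
| 2 placebo | 88% | 0.71 / 0.77 | 0.60 / 0.69 | 0.48 / 0.57 |
| 1 placebo, 1 on 20 mg | 92% | 0.75 / 0.78 | not run | not run |
| 2 on 20 mg | 94% | 0.77 / 0.77 | not run | not run |

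Unadjusted type I error under the plan's rule is about 0.045 with one missing and 0.04 with two. Coverage is 95–96%.

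**The case against.** The strongest reply is that this hardly matters at the planned dropout. If a single loss is equally likely in any arm, a given contrast loses 5.7%, 2.9% or 0% of the effect, about 3% on average, and power falls by about one percentage point on average. Even the worst single loss biases the plan's effect by 0.057 × 1.06 = 0.06 SD, against an SE of about 0.41. The larger figures need two placebo losses, which is above plan. All of this stands.

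The rule also errs in the cautious direction when the doses work about equally. It never inflates false positives, and its root mean squared error is slightly lower (0.405 against 0.417 SD with one placebo patient missing). That is true, but the gain comes from shrinking toward no difference between arms.

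The degrees-of-freedom correction does what Section 24.2 says it is for. With one missing per arm and no effect, the residual SD is 1.002 with it and 0.955 without. What remains is that the contrast still counts 12 per arm and the estimate is unchanged.

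The per-protocol analysis will show the primary endpoint without imputation. It is secondary, however, covers transit only, and also drops patients below 80% compliance. The diary endpoints have no unimputed analysis.

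Finally, the calculations include neither covariates nor the rank transformation that Section 24.1 allows, so the exact percentages could differ under the final model.

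**Conclusion.** The point holds and should be changed, although its size at the planned dropout is small. With equal dose effects and data missing completely at random, one lost patient costs 3–6% of the effect in an affected contrast and at most about 3 points of per-comparison power (about 4 with the gate and Dunnett's test). Two placebo losses cost 12% and about 7–9 points. With clearly unequal doses the bias can run the other way for the weaker dose.

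The harm is an estimate that depends on which arm loses a patient, together with some lost power. It is not a false-positive risk. Neither the plan's rule nor an observed-data analysis handles missingness that depends on the unseen outcome, such as withdrawal for severe diarrhea.

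**What to change.** In Section 24.2, Section 24.9 and the synopsis, make the primary analysis the planned ANCOVA on all randomised patients with an observed response, in their randomised arm, regardless of compliance and without imputation. Keep the overall-mean fill-in as a sensitivity analysis. The new primary analysis is unbiased when missingness is unrelated to the unobserved response given arm and the model covariates.

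Add a second sensitivity analysis for outcome-dependent missingness. Patients withdrawn for diarrhea with no 24-hour geometric center would be given a stated range of fast-transit values, for example 3.0 to 5.0. The upper end is the limit of the 1–5 scale in Section 24.5; the lower end is an assumption and lies above the 2.30 entry ceiling. If such withdrawals cluster on drug, this analysis favours drug, so report it as a range with the number of patients filled in per arm.

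The cost is wording in three places and one line of code. With k covariates and m missing, the residual degrees of freedom are 36 − 3 − k − m under both rules. The price is that a patient without a response does not enter the primary model, so the set must be described as all randomised patients with an observed response. For transit it will overlap heavily with the per-protocol set, differing only in non-compliers.
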